These studies focus on using base (bicarbonate) to titrate high dietary acid load, which is emerging as a new risk factor for disability mediated through the progression of the aging associated-decline of kidney function. We plan to determine the feasibility (this application) and ultimately effectiveness (the subsequent R01) of a comparably simple and generally safe intervention to decrease dietary acid load in elderly, which, in spite of strong evidence in support of its potential effectiveness, has not been tested in the age group who is also most likely to benefit from this intervention and at risk for disability. This intervention may ultimately help protect kidney function and reduce the associated disability in elderly, with a hope that it may work synergistically with exercise, the only other intervention demonstrated in a randomized, controlled clinical trial to ameliorate disability, albeit modestly (the LIFE trial). The importance of the high dietary acid load in face of declining kidney function is a public health issue pointed out ~ 20 years ago, at which time the term "presbyneephria" was coined to alert the medical community to consequences of the diminishing capacity of the aging kidney to excrete acid, including osteopenia, sarcopenia, adverse functional outcomes and disability(30-32).

Data quality and management

The study investigators and staff have experience and expertise in quality control procedures and successful participant tracking in randomized controlled trials. We will use a computerized tracking system to document participant attendance, generate quality control reports for identifying protocol deviations and to assess protocol adherence over time. All data will be entered into web-based forms on a continuous basis as collected, and analysis datasets will be stored in SAS. All data will be examined monthly by histograms and scatterplots to check for internal inconsistencies, unusual data needing further verification, and outliers. Telephone screening and in-person assessment interviews will be conducted by trained study staff who will use computer-assisted technology, entering the data directly into desktop computers.

Data entry is facilitated by automated skip patterns and alerts for out of range values. We will develop standardized reports that will be used for quality control. Careful development of data collection forms is crucial (a) to allow for systematic and uniform recording of participants' data, (b) help maintain complete data collection, and (c) to minimize the possibilities for data entry errors. Data entry screens are created to mimic the forms. Forms are designed so to make data entry easy and straightforward. In addition the above precautions, procedures to monitor screening, data collection, follow-up, clinical measures, forms and data entry will also be used.

Data and Safety Monitoring Plan

We will use the WFU Pepper Center's appointed Data Safety Monitoring Board. This board meets twice a year and reviews all studies that are supported by the WFU Pepper Center. A copy of the report will be reported to the IRB after each meeting.

Informed Consent

Informed consent will be obtained by a trained study coordinator in a clinic room with closed doors. The study interviewers explain the purpose, methods and extent of the study to prospective participants. The potential participant is asked to read the informed consent form and ask questions. We require study staff to review all of the key aspects of the study verbally with the potential participants. Staff is then required to question potential participants to ascertain whether he/she has understood the information. The consent form will only be signed once the participant has read the form and is satisfied with all information given. The person administering consent will also sign and a copy of the signed and dated consent form will be given to the CRU, and to participants, and the original document will be placed in subjects' individual study files, which will be stored in a secure location.

Storage and disposal of biological material

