The study will be conducted at the academic medical center, specifically the Clinical Research Unit (CRU) of the Wake Forest School of Medicine (WFSM) and with the support of the Pepper Center and Translational Science Institute. The participants will be recruited from the general community and evaluated and followed by the CRU.

Subjects selection criteria

Elderly at risk for disability with mild impairment of kidney function will be selected for this study.

Inclusion Criteria	Exclusion Criteria
Age 65+ years of age	Uncontrolled (>160 mg/dl fasting blood glucose), insulin-dependent diabetes and/or uncontrolled hypertension (SBP >160 , DBP >100)
SPPB (short physical performance battery) score >3	a current diagnosis of psychotic disorder or taking anti-psychotic medication
eGFR stage 2 (60-89) or 3 (30-59)	take more than 14 alcoholic drinks per week
	plan to relocate out of the study area within the 8 months
Net endogenous acid production (NEAP) >40 mEq/d	self-reported inability to walk across a room
Willing to provide informed consent and agrees to randomization	those who reside in nursing homes
Not involved in another intervention study	have difficulty communicating with study personnel due to speech or language or hearing problems
	had cancer requiring treatment in the past 1 year
	lung disease requiring regular use of corticosteroids at a dose of >7.5 mg/d for the last 3 months or use of supplemental oxygen
	cardiovascular disease (Class III or IV congestive heart failure)
	significant valvular disease, uncontrolled angina
	myocardial infarction, major heart surgery (i.e., valve replacement or bypass surgery) in past 6 months
	stroke, deep vein thrombosis, or pulmonary embolus in the past 6 months,
	Parkinson's disease or other progressive neurological disorder
	other medical or behavioral factors that in the judgment of the principal investigator may interfere with study participation or the ability to follow the intervention
	clinical judgment concerning safety or noncompliance
	Individuals with BMI <18.5 ; or unintentional weight loss $>4\%$ in last 6 months
	MoCA score under 24
	End Stage Renal Disease (ESRD) on dialysis or primary kidney disease
	Other illness of such severity that life expectancy is less than 12 months
	Any tobacco or nicotine product use in the past year
	Serum HCO ₃ >30 meq/L; serum K ⁺ out of normal range <3.5 or >5.2

Sample Size

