Oral bicarbonate supplementation group. Participants will be advised to continue their usual dietary and exercise pattern, but to take supplementation capsules. They will receive 0.3 meq/kg/day NaHCO₃, a dose based on the literature (14) and our Health ABC cohort preliminary study (8). The dose of 0.3 mg/kg/d NaHCO₃ was reported to reduce net acid excretion ~50% in individuals with similar daily acid load(14), and was effective in decreasing the rate of yearly eGFR decline in patients with hypertensive nephropathy; the dose has also been reported as safe (14, 15). NaHCO₃ will be provided in gelatin capsules containing 10 meq NaHCO₃, so that NaHCO₃ can be dosed to the nearest amount by total body weight; e.g, a 70kg person will receive 2 capsules daily, and an 85kg person would receive 3 capsules daily (14). Adherence will be assessed by pill count. Compliance will be measured at months 3 and 6 by determining the change from the baseline in net acid excreted (NEA) in 4hr-urine; an advantage of our approach is that compliance can be measured objectively rather than estimated. Oral bicarbonate has been used for decades in patients with CKD or distal renal tubular acidosis to treat metabolic acidosis(7), and is generally considered free from significant side effects. Participants will be withdrawn if any of the following occur: total carbon dioxide >30mmol/L, serum K+ <3.5mEq/L, hospitalization for congestive heart failure, weight gain >2kg due to edema, or increase in blood pressure (>15 mmHg systolic or diastolic) (7, 15).

Placebo group. Participants will be advised to continue their usual dietary and exercise pattern, but to take supplementation capsules (methylcellulose). To ensure participants' blinding, identical capsules will be taken and the total number of capsules kept constant. The placebo group will be followed in the same manner as the bicarbonate group; all assessors will be blinded with respect to group assignment.

Clinical assessments, laboratory analysis and analytical tests.

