An 4-hour urine collections were chosen because they can be done during the day in the Clinical Research Unit (CRU). Participants will empty their bladders before beginning the timed collection; then all urine collected over 4hrs will be pooled into a collection container. The specimen will be refrigerated during the collection period and subsequently frozen until analysis. While total urinary nitrogen and Ca⁺² will be done by LabCorp, a trained technician in our Geriatrics laboratory will determine NEA/Cr (urine ammonium + titratable acidity) using standard methods (16).

For blood gas measurements, a blood sample will be obtained from a cannulated hand vein warmed for 10-15 min at 55°C before sampling. Samples will be analyzed immediately after phlebotomy(17), using an ABL5 blood gas analyzer to measure blood pH and pCO₂; based on these measurements, the analyzer calculates serum bicarbonate using Henderson-Hasselbalch equation.

Kidney function will be determined using uACR and eGFRcys. (estimated with CKD Epidemiology Collaboration equation (CKD-EPI) (18), based on serum cystatin c levels, which will be measured by a particle-enhanced immunonephelometric assay86). The Nutrition Data System for Research (NDSR) will be used to conduct 24-hour food recalls. NDSR is a computer-based software application which will be used to assess daily protein and K+ intake needed for calculation of NEAP = [54.5x(prot (g/d) / pot (meq/d)] – 10.2, where

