4hr urine collection to determine (Net acid excretion (NAE); urinary nitrogen and Ca ⁺² excretion, uACR) Urea Nitrogen, Uric Acid, Urine Creatinine,) and obtain urine for storage		X		X	X
Randomization		X			
Urine Metabolomics		X			X
Dispense Medication		X		X	
Medication Adherence				X	X

Outcome Measure(s)

1. Determine the feasibility of achieving ~50% reduction in net acid excretion (NEA/Cr meq/g) following 6 months of oral bicarbonate supplementation, compared to the placebo group
2. Determine
 - a. Recruitment yields
 - b. Adherence to the assessment schedule
 - c. Compliance with intervention over 6 months

- d. Collect data on variability and longitudinal correlation structure of kidney function, lean body mass and functional outcomes
- 3. Ascertain feasibility of using metabolomics to detect changes in kidney function following the intervention

Analytical Plan

All data will be entered as collected into web-based forms; analysis datasets will be stored in SAS. All data will be examined monthly by histograms and scatterplots to check for internal inconsistencies, unusual data needing further verification, and outliers. In few case of outliers and unusual data, participant's charts were reviewed to ascertain whether any adverse measurement conditions or circumstances or potential artefacts existed. Only in cases where measurement artefacts were identified or other circumstances were found that adversely affected data collection were the measurements removed. Otherwise all data remained within the data set. Sensitivity analyses will be performed with and without potential outliers included in individual analyses.

For each analysis, regression diagnostics and exploratory analyses will be performed to find appropriate transformations of the variables, if needed. Priority in choosing a transformation will be to satisfy: 1) linearity, 2) homogeneity, and 3) normality assumptions. Initial analyses will follow the "intent-to-treat" principle. Due to having low power to detect potentially important relationships within this pilot, emphasis will be on using confidence intervals to described estimated parameters and relationships. When hypothesis testing is performed, we will set the significance level at $\alpha=0.05$. We have chosen this level for all hypothesis tests within the pilot because risk of missing an association by making a Type II error outweighs the concern for falsely identifying relationships via a Type I error.

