The nature, purpose, and risks of all procedures and protocols will be explained to each participant prior to obtaining the written consent. All examiners are trained in the standardized conduct of all assessments before data collection. Participants will be instructed to wear appropriate and comfortable clothing and standardized written instructions will be provided prior to each study visit. The primary outcome of interest (change in net acid excretion (NAE) by the kidney) was selected as an indicator of feasibility of implementing this intervention in elderly individuals. Oral bicarbonate will titrate dietary acid load, decrease net endogenous acid production (NEAP) and this will result in decreased acid excretion by the kidney. This dose (0.3mg/kg) was selected according to published studies, which indicated that it is generally safe and can decrease NEA ~ 50%(14). We have extensive experience measuring all of these outcomes in our research studies and the fact that there is such an easy-to-assess and inexpensive (simple chemical titration of titratable acid and ammonium) outcome to measure is an important advantage of our approach. Importantly, decreased NEA will also serve as quantitative measure of compliance.

Sources of Research Material

Participants will self-report personal information on paper survey forms including personal demographic data, race, health information, and psychological and social data. Results will also be recorded in a computer database. Data from the paper forms will be entered into an electronic database on a computer workstation. All material and data will be obtained solely for research purposes.

Potential Risks

The potential risks to study participants receiving bicarbonate supplementation have recently been reviewed by [name] who is a consultant on this study (7). In summary, the potential risks of this study include:

- 1) **Blood Draw.** Participants may experience temporary pain, bruising, bleeding and a small risk of infection or fainting or dizziness during the blood sample collection process. Only trained staff will be responsible for the collection of blood samples.

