- 2) **Metabolic alkalosis (increased serum bicarbonate).** Theoretically, administration of bicarbonate can cause metabolic alkalosis, but that is unlikely because the kidney excretes excess of bicarbonate efficiently. We will be enrolling participants with CKD 2 or 3; at this level of kidney function, the participants should not experience problems with elimination of any excess of bicarbonate. Moreover, it has been demonstrated that oral bicarbonate supplementation for 1 year at 1 meq/kg/bw/day (70 mEq/day for 70 kg =5.9g/d) even in patients with substantially decreased glomerular filtration rate (stage 4 CKD) did not increase serum bicarbonate above normal levels (24). An exception would be a participant who developed e.g. vomiting and hypokalemia because of some unrelated e.g. viral illness. In that case, the participant would be advised to discontinue bicarbonate supplementation until recovery, since these individuals might be susceptible to develop metabolic alkalosis.
- 3) **Volume overload.** Studies that used bicarbonate supplementation for up to 5 years did not report increases in blood pressure or required increased dose of anti-hypertensive agents (7, 24). This is not surprising given that NaCl supplementation, but not sodium bicarbonate supplementation has been shown to affect blood pressure. Regarding other electrolyte and volume abnormalities, we will initially select participants who do not have edema. Nevertheless, the participants will be carefully monitored for edema development. It is important to note that a recent pilot trial, which tested safety and dose of sodium bicarbonate in CKD patients did not find development of edema as a side effect (15). Of interest for our application is that the dose we proposed to use is in the range which according to Abramowitz et al.(15) did not show any difference in adverse effects compared to placebo:

Table 5. Side effect profile before and during treatment

Adverse Effect	Baseline	Placebo	Oral Sodium Bicarbonate Dose (mEq/kg per day)			P Value
			0.3	0.6	1.0	
Gastrointestinal symptoms						
Bloating	3 (15)	4 (20)	2 (10)	2 (10)	4 (22)	0.96
Flatulence	10 (50)	15 (75)	11 (55)	12 (60)	10 (55)	0.39
Stomach upset	3 (15)	4 (20)	3 (15)	3 (15)	3 (11)	0.84
Nausea	3 (15)	2 (10)	0 (0)	3 (15)	4 (22)	0.28
Total	12 (60)	16 (80)	11 (55)	12 (60)	11 (61)	0.24
Edema						0.61
None	11 (55)	12 (60)	13 (65)	11 (55)	10 (55)	
1+	7 (35)	5 (25)	4 (20)	6 (30)	7 (39)	
2+	2 (10)	3 (15)	3 (15)	3 (15)	1 (6)	

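### The formula for net acid excretion has no urine bicarbonate term; if bicarbonate excretion rises on treatment and the titration does not net it out, the treatment effect is understated

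*Combined protocol and SAP*

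**What the plan says.** The section on human subjects involvement names the endpoint: "The primary outcome of interest (change in net acid excretion (NAE) by the kidney"). Item 1 under Outcome Measure(s) sets the target: "Determine the feasibility of achieving ~50% reduction in net acid excretion (NEA/Cr meq/g) following 6 months of oral bicarbonate supplementation". (The document writes both NAE and NEA for the same quantity.)

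The one formula is in the section on clinical assessments and laboratory analysis, where a technician "will determine NEA/Cr (urine ammonium + titratable acidity) using standard methods (16"). The human subjects section echoes it in a remark on how cheap the measurement is: "simple chemical titration of titratable acid and ammonium".

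For the 4-hour urine, the schedule of events lists NAE, urinary nitrogen, calcium and uACR, then "Urea Nitrogen, Uric Acid, Urine Creatinine,) and obtain urine for storage". Neither urine bicarbonate nor urine pH is on that list. A spot urinalysis is scheduled at screening and 6 months, but its components are not given, it is a different specimen, and nothing links it to NAE. The Aim 1 analysis contains no subtraction. Bicarbonate is otherwise measured only in blood.

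Three further statements bear on the point:
- Dose: "They will receive 0.3 meq/kg/day NaHCO₃".
- Entry criterion: "Net endogenous acid production (NEAP) >40 mEq/d".
- Potential Risks, item 2, on why alkalosis is unlikely: "the kidney excretes excess of bicarbonate efficiently".

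**The concern.** Net acid excretion is ammonium plus titratable acid minus excreted bicarbonate. The last term makes it net, and it is absent from the written formula. In most trials the omission would be roughly balanced between arms. Here the intervention is bicarbonate, so any rise in the omitted term is expected in the active arm, and leaving it out can only pull the comparison toward no effect.

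Three results depend on the measure. The first is the Aim 1 contrast at 6 months. The second is the judgement of whether a reduction of about 50% is feasible, which matters because the Analytical Plan puts its emphasis on estimates and confidence intervals. The third is compliance, which the plan proposes to read objectively from the change in NAE at months 3 and 6. A participant who takes every capsule and excretes part of the dose as bicarbonate would look less compliant than is true.

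**Working it through.** **1. The plan's own figure.** Inputs from Sample Size: 16.5 mEq/g (called a change, but usable only as a standard deviation), 35 per group after 12.5% loss (80 × 0.875 / 2 = 35), two-sided alpha 0.05, difference 11.4 mEq/g. A two-sample t calculation gives 81.3% power against the stated 80%; the detectable difference at 80% power is 11.21 with 35 per group and 11.38 with 34. The figure reproduces, so the point is not an error in the power arithmetic.

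**2. Direction.** Let the measured outcome be M = (NH4 + TA)/Cr and the net outcome N = (NH4 + TA - HCO3)/Cr. Let h be the rise in urine HCO3/Cr in the active arm minus the rise in the placebo arm. Then

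measured between-arm fall = net between-arm fall - h.

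If h is positive and not netted out, the measured fall is too small by exactly h.

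**3. Scale (assumed).** The documents give neither urine bicarbonate nor creatinine per collection. Assuming 0.2 g creatinine in 4 hours, 1 mEq of extra bicarbonate in the collection is 1 / 0.2 = 5 mEq/g. If sustained all day, that is 6 × 1 = 6 mEq/d, against a dose of 0.3 × 70 = 21 mEq/d at 70 kg (29%) or 0.3 × 85 = 25.5 mEq/d at 85 kg (24%).

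**4. Effect on the ~50% target and on power.** With baseline B, a true 50% fall reads as (0.5B - h)/B. This assumes no change on placebo and little bicarbonate in the urine at baseline. B = 40 and B = 60 mEq/g are assumptions. Power is by t with 35 per group and SD 16.5, for a true difference of 20 or 30. The plan states that range in meq/d; it is taken here as mEq/g.

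| h (mEq/g) | mEq per collection | 50% reads as, B = 40 | 50% reads as, B = 60 | Power, true 20 | Power, true 30 |
|---|---|---|---|---|---|
| 0 | 0 | 50% | 50% | 99.9% | ≥99.9% |
| 1 | 0.2 | 47.5% | 48.3% | 99.7% | ≥99.9% |
| 2 | 0.4 | 45% | 46.7% | 99.4% | ≥99.9% |
| 5 | 1.0 | 37.5% | 41.7% | 96.3% | ≥99.9% |
| 10 | 2.0 | 25% | 33.3% | 70.5% | ≥99.9% |

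For example, at h = 5: (20 - 5)/40 = 37.5% and (30 - 5)/60 = 41.7%. The estimate set against the target is more sensitive than the hypothesis test.

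**The case against.** The strongest reply is that no bias has been shown.

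- **The assay may already be net.** The formula defers to a cited standard method, and the documents do not say whether that titration nets out bicarbonate. This stands, and it is why the point is conditional. It does not excuse the written formula, which is the only one a reader or a laboratory has to follow.
- **The dose is below the acid load.** At 21 to 25.5 mEq/d against an entry NEAP above 40 mEq/d, the average participant still has acid to excrete, so bicarbonate loss may be small. The risk-section sentence says what happens to an excess, not that this dose leaves one. This stands as a reason to expect a modest effect. It does not make the effect zero in a 4-hour daytime collection whose timing relative to the capsules is not stated.
- **The ~50% benchmark may be on the same scale.** It comes from a cited published trial. If that trial also measured ammonium plus titratable acid, target and measurement match. The documents do not say. Even then, the outcome would not be net acid excretion.
- **Power is ample.** This is largely right at the planned difference. The 11.4 mEq/g figure is the smallest detectable difference, not the expected effect, and is the wrong yardstick here.

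A reader might also infer a much larger bias from urine pH. With pK 6.1, pCO2 40 mmHg, 0.5 L of urine and 0.2 g creatinine, bicarbonate of 0.98, 3.08 and 9.75 mEq/L at pH 6.0, 6.5 and 7.0 becomes 2.4, 7.7 and 24.4 mEq/g, so a shift from pH 6.0 to 7.0 would hide 22 mEq/g. The arithmetic is sound but the top of that range is not supported. It means 22 × 0.2 = 4.4 mEq per collection, or 26.4 mEq/d if sustained, which exceeds the whole weight-based dose at 70 or 85 kg and is 88% of the 30 mEq in three capsules. A short peak after a dose cannot be excluded, but the documents give no basis for assuming one.

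**Conclusion.** The point holds in conditional form. The stated formula for the primary outcome is not net, and nothing planned on the 4-hour urine would supply the missing term. If bicarbonate excretion rises more on active treatment than on placebo, and the titration does not net it out, the Aim 1 difference, the percentage set against the ~50% target and the NAE-based compliance measure are too small by that amount.

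The direction follows from algebra; the size is unknown. The illustration of 5 mEq/g, with a true 50% fall reading as 37.5% to 41.7%, rests on assumed values for creatinine (0.2 g per 4 hours), extra bicarbonate (1 mEq per collection) and baseline (40 to 60 mEq/g). At that size, power for a true difference of 20 to 30 is about 96% or more; it falls to 70.5% only for a true difference of 20 with 10 mEq/g hidden.

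Two stronger conclusions are tempting. One is that the fall in the bicarbonate arm definitely is understated. The documents support neither a given amount of bicarbonate in the urine nor a particular behaviour of the cited assay. The other is that every planned correlation involving NAE is distorted. Baseline correlations, taken before any capsule, should be largely unaffected; only those using follow-up values or changes in NAE could be.

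**What to change.** Wherever the outcome is defined (the laboratory section and the human subjects section), write NAE/Cr = (ammonium + titratable acid - bicarbonate)/creatinine, and state that negative values are allowed and kept in the analysis.

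Obtain the bicarbonate term by titration on the existing 4-hour specimen. For example, acidify, remove CO2 and back-titrate, so that titratable acid minus bicarbonate is measured directly. Do not calculate it from pH and pCO2 on stored urine: the specimen is pooled over 4 hours, refrigerated and then frozen, with no step described to preserve CO2.

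If the laboratory's titration already nets out bicarbonate, the assay needs no change; correct the stated formula to match it.

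Cost: a wording change and at most one added titration step per sample. With 4-hour urine at baseline, 3 months and 6 months, that is no more than 83 × 3 = 249 samples. No participants or visits are added.

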Based on published studies(11-14), we have assumed a 6-month change in NAE/Cr within groups of 16.5 mEq/g. Assuming a conservative 12.5% loss-to-follow-up at 6 months (35 participants/group), we will have 80% power to detect a difference between groups in NAE/Cr as small as 11.4 mEq/g with a two-sided, Type I error rate of 0.05. Considering that expected change in NEA/Cr will be about 20-30 meq/d(11, 12, 14), we should be able to detect clinically important changes in NEA/Cr from the proposed intervention. For Aim#2, we are interested in estimating recruitment yields, compliance and other parameters that will inform the feasibility of a full-scale trial. With up to 83 participants recruited, we will be able to estimate the two-sided, 95% Clopper-Pearson Exact confidence interval with a width of 0.043 if the recruitment yield is 10%, and a width of 0.14 if the recruitment yield is 40%. For correlational analyses, 83 participants will allow us to detect correlation coefficients of 0.31 or larger with at least 80% power assuming a 2-sided 0.05 □.

Interventions and Interactions

Patients will be screened over the phone and in the clinic to see if they meet qualifications for the study. Once screened, they will be randomized into one of two groups- taking an oral bicarbonate supplement or a placebo.

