Aim 1 Determine the feasibility of achieving ~50% reduction in net acid excretion (NAE/Cr meq/g) by the kidney after 6-months of oral bicarbonate supplementation vs. placebo. (NAE/Cr was measured at each visit.)

We will use mixed effects analysis of covariance (ANCOVA) to estimate change in NAE/Cr within randomized groups, including the baseline value of NAE/Cr and the intervention effect in the model. A contrast will be used to obtain estimates and 95% confidence intervals after 6-months. This approach utilizes all measurements obtained during follow-up and can provide unbiased estimates, if missing outcomes are related to outcomes obtained at other time points.

Aim 2 Ascertain recruitment yields, adherence to the intervention, adherence to the assessments, and sustainability of the intervention over 6 months; and collect data on variability and longitudinal correlations in kidney function, lean body mass, and functional outcomes to design a future full-scale clinical trial.

For recruitment yields, we will calculate the proportion of screened participants randomized, overall, and within gender and ethnic subgroups.

Adherence to the intervention will be measured as the proportion of the prescribed dose (bicarbonate or placebo) taken, based on pill counts.

Compliance with assessments will be determined by calculating proportion lost to follow-up at each visit and the percent of missing measurements.

Sustainability of the intervention will be assessed via: a) generalized estimating equations for repeated measures on the proportion of expected pills a participant took.

Means (proportions), variances, and 95% confidence intervals (exact CI where needed) will be calculated within intervention groups and for the difference between groups for all endpoints.

Correlations coefficients (both Pearson and Spearman) will be used to investigate the association between net endogenous acid production (NEAP) and other measures of interest, as well as changes in net acid excretion

(NAE) and measures of interest. (Measures of interest: tCO₂, blood bicarbonate (blood gas), eGFR, urineACR, SPPB, 400m walk, bone density).

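### Aim 1 asks about a relative reduction of about 50% in NAE/Cr versus placebo, but the planned intervals and the power are absolute, and no interval for the percentage is planned

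*Combined protocol and SAP*

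**What the plan says.** The target is relative. Outcome Measure(s), item 1, reads "Determine the feasibility of achieving ~50% reduction in net acid excretion (NEA/Cr meq/g) following 6 months of oral bicarbonate supplementation", with the placebo group as comparator. The Objectives and the Aim 1 heading of the Analytical Plan set the same goal.

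The analysis is on the absolute scale:
- **Analytical Plan, Aim 1.** A mixed-effects ANCOVA is used "to estimate change in NAE/Cr within randomized groups, including the baseline value of NAE/Cr and the intervention effect in the model". Then: "A contrast will be used to obtain estimates and 95% confidence intervals after 6-months". No ratio or percentage is named.
- **Analytical Plan, Aim 2.** "95% confidence intervals (exact CI where needed) will be calculated within intervention groups and for the difference between groups for all endpoints".
- **Sample Size, repeated in the Analytical Plan's power paragraph.** "we will have 80% power to detect a difference between groups in NAE/Cr as small as 11.4 mEq/g".

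Three other statements bear on the point. The Analytical Plan says that "emphasis will be on using confidence intervals to described estimated parameters and relationships", because power is low in a pilot. It also says that "regression diagnostics and exploratory analyses will be performed to find appropriate transformations of the variables, if needed", with linearity, homogeneity and normality as the criteria. Human Subjects Involvement and Characteristics says: "The primary outcome of interest (change in net acid excretion (NAE) by the kidney) was selected as an indicator of feasibility".

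**The concern.** The trial's first question is whether the reduction is about half. An absolute difference with its interval does not answer that until it is set against a placebo level, and that level is itself estimated with error. The percentage that will be reported for Aim 1 is therefore a quantity for which this interval-focused plan provides no interval. A ratio with an interval would appear only if diagnostics happened to lead to a log transformation, and the criteria for transforming have nothing to do with the relative target.

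At stake is how clearly the pilot can answer its own feasibility question. The same absolute result can be compatible with the target or exclude it, depending on the placebo mean.

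**Working it through.** **1. Reproduce the plan's figure.** Inputs from Sample Size: 16.5 mEq/g, 35 per group, difference 11.4 mEq/g, two-sided 0.05. The text calls 16.5 a change, but it reproduces the power when read as a within-group SD, so I read it that way. SE of the difference = 16.5 x sqrt(2/35) = 3.94, and 11.4/3.94 = 2.89. The t test with 68 df gives power 81.3%, against 80% stated. The smallest detectable difference at 80% power is 11.2, against 11.4 stated. The absolute calculation stands.

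**2. What 11.4 mEq/g means as a percentage.** The documents give no placebo or baseline NAE/Cr. The expected change is printed as 20-30 meq/d. If that is about 50%, the reference level is 40-60 meq/d, or 40-60 mEq/g at an assumed 1 g creatinine per day. At 0.7-1.5 g/day the range widens to 40/1.5 = 27 up to 60/0.7 = 86 mEq/g. These levels are assumptions.

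| Placebo mean (mEq/g) | 11.4 as a reduction |
|---|---|
| 22.8 | 50% |
| 30 | 38% |
| 40 | 29% |
| 60 | 19% |

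**3. Precision of the adjusted means.** Further assumptions: baseline to month-6 correlation 0.5, equal SDs in both arms, 35 per arm analysed.
- Residual SD = 16.5 x sqrt((1 + 0.5)/2) = 14.29.
- SE of each adjusted mean = 14.29/sqrt(35) = 2.42.
- SE of the difference = 2.42 x sqrt(2) = 3.42.
- With t(0.975, 67) = 1.996, the half-width of the absolute interval is 6.8 mEq/g.

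**4. Interval for the relative reduction.** Let R be the ratio of adjusted month-6 means, bicarbonate over placebo. By the delta method, SE(R) = (2.42/placebo mean) x sqrt(1 + R^2).

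| Difference | Placebo mean | Reduction | 95% CI |
|---|---|---|---|
| 20 | 40 | 50% | 37-63% |
| 20 | 60 | 33% | 24-43% |
| 30 | 60 | 50% | 41-59% |
| 10 | 40 | 25% | 10-40% |

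The first two rows share the absolute result 20 +/- 6.8. One is centred on the target and the other excludes it. In 10,000 simulated trials with a true 50% reduction, the delta interval covered the truth in 95.1% (placebo mean 40) and 94.8% (60).

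**5. A true reduction of half the target (25%).** Share of trials with a significant absolute difference, under the assumptions of step 3:

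| Placebo mean | True difference | Significant |
|---|---|---|
| 22.8 | 5.7 | about 37% |
| 30 | 7.5 | about 58% |
| 40 | 10 | about 82% |
| 60 | 15 | about 99% |

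In the same setting the ratio interval excludes 50% in 93% of trials at a placebo mean of 40, and in more than 99% at 60. With correlations of 0.3 and 0.7 at a placebo mean of 40, the share significant is 87% and 77%.

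**6. Does the route to an interval matter?** For an observed 20 of 40:
- ratio of adjusted means: 37-63%;
- ratio of unadjusted arm means: about 34-66%;
- absolute interval divided by the placebo mean: (20 +/- 6.8)/40 = 33-67%. This is wider by sqrt(2)/sqrt(1.25) = 1.26 and covers 98.6% rather than 95%.

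**The case against.** The strongest reply is that little is lost. Group means and their intervals are planned for all endpoints, so anyone can form the percentage and, with a little work, an interval. That is correct, and it limits the point to a gap that planned output can close.

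A reader might infer that the choice among after-the-fact routes would decide the answer. The figures do not bear that out. The three intervals in step 6 lead to the same reading. With a true 50% reduction, the crudest route and the delta interval disagree about excluding 50% in about 4% of trials. The largest disagreement found was 15% (true reduction 33%, placebo mean 40). The choice matters only at the margin.

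A reader might also infer that the plan would take a significant difference as proof of a 50% reduction. No section says so, and the plan stresses intervals over tests. The absolute interval can itself be informative: 10 +/- 6.8 gives 3.2 to 16.8, which excludes 20, half of a placebo mean of 40. Nor is an effect of half the target size always likely to be significant. Step 5 shows that this depends on a placebo mean that the documents do not give.

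Finally, the target wording could mean percent change from baseline compared between arms, which would differ from the ratio of month-6 means if placebo drifts. That ambiguity is real, and it is a reason to define the percentage in advance.

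**Conclusion.** The point holds as a scale mismatch with a missing interval. The aim is relative, the planned NAE/Cr intervals and the power are absolute, and an interval for the relative reduction could arise only through a data-driven transformation. This part rests on the text alone.

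Its size is conditional on 16.5 mEq/g being the SD of change, a correlation of 0.5, equal SDs, 35 per arm and an assumed placebo mean. Under those inputs a difference of 20 mEq/g is 50% (37-63%) at a placebo mean of 40 and 33% (24-43%) at 60, so the absolute result alone does not answer Aim 1.

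A reader might infer that the trial is undersized or its primary estimate invalid. The documents do not support that: the stated power reproduces at 81.3%, and the absolute change is the named primary outcome. This change should be made because it gives the trial's own question an interval at almost no cost.

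**What to change.** Keep the planned absolute difference with its 95% CI, since change in NAE is the named primary outcome. Beside it, pre-specify for Aim 1 the relative reduction versus placebo at month 6: 1 minus the ratio of adjusted month-6 mean NAE/Cr (bicarbonate over placebo) from the planned model. Give it a 95% CI by one named method (delta, Fieller or bootstrap) and read it against about 50%. If the model is fitted to change, the month-6 mean is the adjusted mean change plus the overall baseline mean at which it is evaluated. State in the SAP that this between-arm ratio, and not percent change from baseline, is the definition of the Aim 1 percentage.

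The cost is SAP wording and a few lines of code, with no new data and no change in sample size. These three methods need no log transformation, so zero or negative NAE values are not an obstacle. The one limitation is that the placebo mean must lie well away from zero. Under the assumed inputs it is 40/2.42, or more than 16 standard errors, away at a placebo mean of 40, and 22.8/2.42, or about 9, at 22.8.
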